11. HANDLING OF MISSING OR INCOMPLETE DATES FOR ADVERSE EVENTS AND CONCOMITANT MEDICATIONS

11.1 Imputation Rules for Partial or Missing Stop Dates

If the month and year are present, impute the last day of the month. If only the year is present, impute December 31 of that year. If the stop date is entirely missing, assume the event or medication is ongoing. If a partial or complete stop date is present and the ‘ongoing’ or ‘continuing’ box is checked, then it will be assumed that the AE or concomitant medication stopped and the stop date will be imputed, if partial.

		Stop Date						
		Complete: yyyymmdd		Partial: yyyymm		Partial: yyyy		Missing
Start Date		<1 st Dose	≥1 st Dose	<1 st Dose yyyymm	≥1 st Dose yyyymm	<1 st Dose yyyy	≥1 st Dose yyyy	
Partial: yyyymm	=1 st Dose yyyymm	2	1	2	1	N/A	1	1
	≠ 1 st Dose yyyymm		2		2	2	2	2
Partial: yyyy	=1 st Dose yyyy	3	1	3	1	N/A	1	1
	≠ 1 st Dose yyyy		3		3	3	3	3
Missing		4	1	4	1	4	1	1

1 = Impute the date of first dose

2 = Impute the first of the month

**Statistical Analysis Plan (SAP)
for Clinical Study AP-017**

3 = Impute January 1 of the year

4 = Impute January 1 of the stop year

Note: For subjects who were never treated (first dose date is missing), partial start dates will be set to the first day of the partial month.

Note: If the start date imputation leads to a start date that is after the stop date, then do not impute the start date.

**Statistical Analysis Plan (SAP)
for Clinical Study AP-017**

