5.2 Assessment Methods

Demographic Data

Demographic data will be collected from medical records: age, gender, race, height and weight, comorbidities.

Medical History

Medical history and pre-existing conditions will be collected from medical records.

Concomitant Medications

Concomitant medications will be collected from the medical records: prior (pre-hospitalization) concomitant medications, in-patient concomitant medications.

Mortality

All-cause mortality will be recorded at hospital discharge, Days 28 and 60, as applicable. Cause of mortality will be assessed and documented. All-cause mortality is calculated for the primary endpoint as the percentage of participants with a successful outcome (life) or unsuccessful outcome (death).

Length of Stay (LOS)

Due to the COVID-19 health emergency, the Centers for Medicare and Medicaid is temporarily allowing long-term care facilities not normally used as a resident's room to accommodate beds and residents for care in emergencies/situations needed to help with surge capacity. Therefore, hospitalization refers to hospital and/or inpatient care during the COVID-19 health emergency. Inpatient care may include hospitals treating COVID-19 patients; dedicated COVID-19 treatment facilities with 24/7 care; and/or dedicated research facilities with 24/7 care.

Dates of hospitalization and ICU admission as well as discharge dates will be recorded at hospital discharge, Days 28 and 60, as applicable. The hospital LOS and ICU LOS will be calculated as follows:

- ICU admission: defined (in days) as the first study day when ICU status is changed to “yes” minus baseline date + 1
- Hospital LOS: is defined (in days) as the date of hospital discharge minus date of hospital admission + 1
- ICU LOS: defined (in days) as the date moved out of ICU minus first study date when ICU admission changed to “yes” + 1

Oxygen Use

Oxygen use measured as blood oxygen saturation (SpO2) and oxygen flow rate (liters per minute, lpm) will be recorded at every visit from baseline to Day 5.

Intubation/Extubation

Date and time of intubation/extubation and days on ventilator will be recorded at hospital discharge, Days 28 and 60, as applicable. Proportion of participants who progress to respiratory failure (i.e., need for mechanical ventilation, ECMO, non-invasive ventilation, or high-flow nasal cannula oxygen) will be evaluated.

Vital Signs

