9.3 Data presentation

9.3.1.1 Demographic and Baseline Characteristics:

Demographic (e.g., age, sex, race, ethnicity) and baseline characteristics (e.g., weight, height, comorbidities) summarized using descriptive statistics, overall and by treatment group for the ITT and safety analysis population.

9.3.1.2 Medical History and Physical Examination:

The number and percent of participants with past and current medical disorders at the time of randomization will be presented overall and by treatment group for the ITT and safety analysis population.

9.3.1.3 Concomitant Medications or Treatments:

The number and percent of subjects receiving concomitant medications or therapies prior to and during the study and at the final visit will be tabulated and presented overall and by treatment group for the ITT analysis population.

Concomitant medications/treatments will be summarized using descriptive statistics and will be presented by type of drug (WHO DRUG classification) overall and by treatment group for the safety and ITT analysis populations. There should be no significant differences in the use of concomitant treatments between groups. All concomitant therapies will be recorded to be able to compare any inadvertent imbalances between the groups.

9.3.1.4 Safety Data:

Safety data will be presented by treatment arm. Safety data will be evaluated by changes in vital sign measurements, laboratory assessments, and the frequency and severity of AEs. Concomitant medication will be recorded for safety. AEs will be collected from baseline to Day 60. The severity of AEs (mild, moderate, severe), relatedness (related, possibly related, unrelated) along with the duration, action taken, and outcome (e.g., study withdrawal) will also be recorded.

All data collected under this study protocol will be included in the assessment of patient safety. Missing or incomplete AE data will assume greatest relationship to study drug and/or severity.

Remaining safety data will be collected from enrollment through index hospitalization until hospital discharge (or in-hospital death). Safety data will be tabulated and presented overall and by treatment group for the safety analysis population.

9.3.1.5 Efficacy Data:

The efficacy of treatment on the clinical course and outcome of COVID-19 will be evaluated by treatment arm. Summaries will be performed by severity (severe or critical), individually, and combined.

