7.1 Handling of Missing and Incomplete Data

Incomplete adverse event and concomitant medication dates will be imputed as described in Section 11. If imputed dates are used, then they will be identified as such in the final study report. If an AE start date is missing or partially missing and no additional information is available from the site in order to establish whether the event started before or after the dose of study drug, the event will be considered to have started after dose. Partially missing dates where the month and year is prior to Day 0 will not be classified as post dose.

For the primary effectiveness endpoint analysis, need for mechanical ventilation or death prior to Day 28, a sensitivity analysis will be performed for all patients that have been discharged from the hospital, cannot be reached via telephone contact, and their death status is not known. The sensitivity analysis will be performed where missing mechanical ventilation or death status at Day 28 will be replaced as having died.

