10.3 Safety

10.3.1	Overall Summary of Treatment-Emergent Adverse (TEAE) Events
10.3.2	Incidence of TEAEs by System Organ Class and Preferred Term
10.3.3	Incidence of Treatment-Emergent Related AEs by System Organ Class and Preferred Term
10.3.4	Incidence of Treatment-Emergent Serious Adverse Events (SAEs) by System Organ Class and Preferred Term
10.3.5	Incidence of TEAEs by Preferred Term in Descending Order of Frequency
10.3.6	Incidence of Treatment-Emergent Related AEs by Preferred Term in Descending Order of Frequency
10.3.7.1	Summary of Hematology
10.3.7.2	Summary of BioChemistry
10.3.8.1	Summary of Pulse and Change from Baseline over Time (bpm)
10.3.8.2	Summary of Body temperature and Change from Baseline over Time (F)
10.3.8.3	Summary of Systolic BP and Change from Baseline over Time (mmHg)
10.3.8.4	Summary of Diastolic BP and Change from Baseline over Time (mmHg)
10.3.8.5	Summary of respiration rate and Change from Baseline over Time
10.3.9.1	Concomitant Medication Use by ATC Level 1
10.3.9.2	Concomitant Medications Preferred Term in Descending Order of Use
10.3.9.3	Medication Started on Study Preferred Term in Descending Order of Use

Statistical Analysis Plan (SAP) for Clinical Study AP-017

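### The SAP's single start-date table can turn home and admission drugs with incomplete start dates into medications started on study

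*SAP*

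**What the plan says.** SAP 7.1 sends both kinds of record to the same rules: "Incomplete adverse event and concomitant medication dates will be imputed as described in Section 11". The heading of SAP 11.1 mentions only stop dates, but its table also sets start dates, through four codes. The ones that matter most here are "1 = Impute the date of first dose", "2 = Impute the first of the month" and "4 = Impute January 1 of the stop year"; code 3 is January 1 of the recorded year. The row for a start known only to the month of first dose reads "1 st Dose yyyymm 2 1 2 1 N/A 1 1". Its seven entries are the codes for a complete, month-only and year-only stop date (each split into before first dose and on or after it), and last for a missing stop date. A wholly missing stop date is taken to mean ongoing.

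Two outputs depend on the result. Table 10.3.9.3 is "Medication Started on Study Preferred Term in Descending Order of Use", and SAP 8.4.2 tabulates medication use before the study, during it and at the final visit. The SAP defines neither prior nor started-on-study medication.

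Protocol 5.2 collects medications from the records in two categories, "prior (pre-hospitalization) concomitant medications, in-patient concomitant medications". Protocol 5.1.2 lists concomitant medications among the Day 0 procedures, before treatment. Protocol 9.3.1.3 gives the purpose: "All concomitant therapies will be recorded to be able to compare any inadvertent imbalances between the groups".

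**The concern.** For an adverse event that cannot be dated, assuming onset at first dose errs on the safe side, and SAP 7.1 states that principle for adverse events. It offers no such reasoning for medications. A drug that is ongoing with no known start is, if anything, likely to be background treatment, yet the table dates it to the day study drug began. The same happens to a treatment begun on admission and recorded only by month, if first dose fell in that month. Screening opens no more than three days before Day 0, so the two will usually share a month.

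At stake is how the medication tables read. Permitted background treatment includes remdesivir and dexamethasone. A reader who wants to know whether such treatment was in place before study drug, or was added after randomisation, would look to the prior-use summary and to Table 10.3.9.3. The rule can remove true entries from the first and add false ones to the second.

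**Working it through.** The plan states no figure on this point, so the check is to read the SAP 11.1 table cell by cell and follow example records through it.

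**Step 1: codes by row.** Blank cells in the last two rows are read as that row's own code; this does not affect the first three rows.

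| Start date as recorded | Stop before first dose (full / month / year) | Stop on or after first dose (full / month / year) | Stop missing | Cells with code 1 |
|---|---|---|---|---|
| Month of first dose only | 2 / 2 / N/A | 1 / 1 / 1 | 1 | 4 of 6 |
| Year of first dose only | 3 / 3 / N/A | 1 / 1 / 1 | 1 | 4 of 6 |
| Missing | 4 / 4 / 4 | 1 / 1 / 1 | 1 | 4 of 7 |
| Another month only | 2 / 2 / 2 | 2 / 2 / 2 | 2 | 0 of 7 |
| Another year only | 3 / 3 / 3 | 3 / 3 / 3 | 3 | 0 of 7 |

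In the first three rows, code 1 applies in 4 + 4 + 4 = 12 of 6 + 6 + 7 = 19 applicable cells. With the stop date on or after first dose, or missing, it applies in 12 of 12. With the stop date before first dose it applies in 0 of 2 + 2 + 3 = 7. The stop date therefore decides the outcome.

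**Step 2: example records.** Assume first dose on 15 March 2022.

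- Home drug, start missing, ongoing: code 1, start 15 March 2022.
- Drug begun on admission, start recorded as March 2022, stopped 24 March: code 1, start 15 March 2022.
- Drug with start recorded as 2022 only, ongoing: code 1, start 15 March 2022.
- Start missing, stop recorded as March 2022, true stop 10 March: code 1, start 15 March 2022. The stop-date rule then sets the stop to 31 March, although the drug had ended before first dose.
- Home drug, start recorded as 2019, ongoing: code 3, start 1 January 2019.
- Home drug, start recorded as January 2022, ongoing: code 2, start 1 January 2022.
- Start missing, stopped 10 March 2022: code 4, start 1 January 2022.

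The first four records land on the first-dose date. The last three stay before it, as they should.

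**Step 3: from imputed date to table.** SAP 4.11 and 4.12 give study day = date − date of first dose + 1, so an imputed start falls on Study Day 1. Whether it enters Table 10.3.9.3 depends on a cut-off that the SAP does not state:

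- start on or after randomisation, or on or after first dose: the record enters, and it leaves prior use;
- start strictly after first dose: the record does not enter.

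The stop-date columns of the table split at before versus on or after first dose, which puts the first-dose date on the later side. The on-or-after reading is thus the natural one, but it is an inference.

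**Step 4: size.** The documents give no rate of incomplete medication dates, so the number of misplaced records cannot be calculated. As a unit conversion only: for each 1% of the planned 200 patients whose record for a given drug meets the condition, 200 × 0.01 = 2 entries move on that drug's line.

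**The case against.** The strongest reply is that this concerns few records and has little consequence. Much of that stands.

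- Protocol 7.3 requires start and stop dates, and Protocol 10.7.1 provides for checks at data entry and discrepancy queries. Nothing in the documents shows that dates will often be incomplete.
- A reader might infer that all home drugs and admission treatments are counted as started on study. The table does not support that. Complete dates are kept, a known earlier month or year stays before first dose, and a drug known to have stopped before first dose gets an earlier start.
- A reader might also infer that a real difference between arms in new treatment would be diluted and the power to detect it lost. The plan makes no such test: SAP 8.4.2 describes medications, and the protocol's wish to compare the arms names no method. Table 10.3.9.3 has one line per preferred term, so a misdated home drug inflates its own line and not that of another drug.
- Tables 10.3.9.1 and 10.3.9.2 still count a drug in use at first dose as used, whatever start it is given, and Listing 8 shows baseline medication.
- SAP 7.1 promises to identify imputed dates in the final report.

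These points narrow the concern but do not remove it. Identifying an imputed date does not reclassify the record. The listings named in SAP 10.2 include baseline medication but none devoted to on-study medication, where a reader could undo the error. The missing definition of started on study is itself a gap.

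The opposite blanket rule, treating every incomplete start as prior, would also be wrong. If first dose falls on the 3rd of a 31-day month, 31 − 3 = 28 days of that month lie after it, and true in-patient starts recorded only by month would vanish from the on-study table.

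**Conclusion.** The point holds as a minor one. For medications with a missing, same-month or same-year-only start, and a stop date on or after first dose or missing, SAP 11.1 always assigns the first-dose date (12 of 12 cells). If started on study means on or after randomisation or first dose, home drugs and admission treatments with such dates enter Table 10.3.9.3 and drop out of prior use. This is a misclassification produced by a stated rule, beyond the missing definitions.

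Its extent is unknown, because it depends on how many dates are incomplete and on the undefined cut-off. It touches descriptive medication tables only. The primary analysis, the secondary analyses and the adverse-event comparison are unaffected, and the documents give no basis for a power figure.

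**What to change.** In SAP 11.1, restrict code 1 to adverse events and correct the heading so that it covers start dates. In SAP 4 or 8.4.2, define prior, concomitant and started-on-study medication, and say on which side of the cut the first-dose date falls.

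For a medication whose incomplete start date could precede first dose, classify from data the trial already collects:

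- recorded as pre-hospitalization, or in use in the Day 0 record: prior/ongoing;
- otherwise: query the site;
- still unresolved: show in a flagged start-unknown row, not as started on study.

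The cost is a few definitions, one extra rule and a small programming change. The downside is that a few records remain unknown. No new data collection is needed.

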12. SCHEDULE OF ASSESSMENTS AND PROCEDURES

Visits will be conducted as described:

	Screen	Treatment					Hospitalization/ Continued Care	Follow-Up					
		-3 to 0	0	1	2	3	4	5	Every day until Day 7	7	14	28	60
Study Day													
Visit Window (± days)	--	--	--	--	--	--	--	--	--	--	--	3	3
COVID-19 diagnosis	X												
Informed consent	X												
Medical history and pre-existing conditions	X												
Inclusion/exclusion criteria	X	X											
Urine pregnancy test ¹		X											
Demographics		X											
Randomization		X											
IV treatment			X	X	X	X	X						
Vital signs		X	X	X	X	X	X		X				
Blood oxygen saturation		X	X	X	X	X	X		X				
ECG monitoring (telemetry) ²		X	X	X	X	X	X		X ²				
Hematology ³		X		X		X	X		X ³				
Biochemistry ²		X		X		X	X		X ³				
Cytokine/chemokine assay ⁴		X					X		X ⁴				
Mortality									X			X	X
Ordinal scale for clinical status		X	X	X	X	X	X		X	X	X	X	X
NEWS2 score for clinical status		X	X	X	X	X	X		X	X		X	X
Hospital LOS and ICU LOS			X	X	X	X	X		X			X	X
Date of intubation/ extubation, days on ventilation			X	X	X	X	X		X			X	X
Concomitant medications		X	X	X	X	X	X		X			X	X
Adverse events		X	X	X	X	X	X		X			X	X

¹ As applicable

² Telemetry monitored as needed for patients who have events or abnormal readings requiring measurements.

³ Hematology and biochemistry tests are performed at baseline and every other day through treatment and inpatient stay unless an abnormal value is observed. In the case of an abnormal lab result, continue to collect and test those samples to follow subject through resolution.

⁴ Cytokine and chemokine assays are collected at baseline before treatment, at Day 5 after treatment, and at discharge.

**Statistical Analysis Plan (SAP)
for Clinical Study AP-017**

13. GLOSSARY OF ABBREVIATIONS

AE	Adverse event
ALI	Acute lung injury
ARDS	Acute respiratory distress syndrome
BP	Blood pressure
CDC	Centers for Disease Control and Prevention
COPD	Chronic obstructive pulmonary disease
COVID-19	Coronavirus disease 19
CRO	Contract research organization
DSMB	Data and safety monitoring board
EC	Ethics committee
ECMO	Extracorporeal membrane oxygenation
eCRF	Electronic case report form
EDC	Electronic data capture
EMR	Electronic medical record
EUA	Emergency use authorization
HSA	Human serum albumin
ICH	International conference on harmonization
ICU	Intensive care unit
IRB	Investigational review board
ITT	Intent to treat
IV	Intravenous
LAR	Legally authorized representative
LOS	Length of Stay
NEWS	National Early Warning Score
q12	Every 12 hours
RCT	Randomized controlled trial
SAE	Serious adverse event
SOP	Standard operating procedure
SpO2	Blood oxygen saturation
TNF α	Tumor necrosis factor alpha
WHO	World Health Organization

**Statistical Analysis Plan (SAP)
for Clinical Study AP-017**

15. VERSION HISTORY

Number	Effective date	Version (Principal changes from previous version)
Version 1.0	10 Feburary 2022	Original
